4.2.1.2.6 Serious Adverse Events

An event will be considered as a serious event if "Yes" is checked for "Serious" in the CRF. SAEs will be analyzed throughout the study using the following periods:

- Within 7 days
- Within 30 days
- During the study (i.e., all SAEs occurred during the study)

4.2.1.2.7 Adverse Events of Special Interest

An event will be considered as an AESI if "Yes' is checked for "Is the event an AESI?" in the CRF.

AESIs will be analyzed throughout the study using the following periods:

- Within 7 days
- Within 30 days
- During the study (i.e., all AESIs occurred during the study)

4.2.2 Other Safety Endpoints

4.2.2.1 Pregnancy

This information will not be included in the analysis but will be listed separately. No derivation or imputation will be done.

4.2.2.2 Action Taken

This information will be summarized as collected, including missing observations. No derivation or imputation will be done.

4.2.2.3 Seriousness

This information will be summarized as collected. No derivation or imputation will be done.

4.2.2.4 Outcome

This information will be summarized as collected. No derivation or imputation will be done.

4.2.2.5 Causal Relationship

This information will be summarized as collected in the field "Relationship to study vaccine". Missing causal relationship will be handled as described in Section 3.4.4.1.2.. Relationship to study procedure is only presented in the listing.

4.2.2.6 Adverse Events Leading to Study Discontinuation

This information will be summarized as collected. A flag is available in the clinical database for all AEs in order to identify AEs leading to discontinuation before the end of active phase. In general, the items that are counted are:

- Disposition table: A participant who, on the "Completion at End of Study" form question "What was the participant's status?" has "Adverse Event" checked.
- Safety overview table: A participant who has either on the "Completion at End of Study" form, question" What was the participant's status?" has "Adverse Event" checked or lists a solicited AE that has "Caused Study Termination" checked that is at least Grade 1 or an unsolicited AE that has "Caused Study Discontinuation" checked that is at least Grade 1 or missing and is within the time period indicated.
- System Organ Class (SOC)/Preferred Term (PT) table: A solicited AE that has "Caused Study Termination" checked that is at least Grade 1 or an unsolicited AE that has "Caused Study Discontinuation" checked that is at least Grade 1 or missing and is within the time period indicated.

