3.4.4.1.3 Intensity

For solicited reactions, missing intensities will be handled as described in Section 4.2.1.1.1. For unsolicited AEs, missing intensities will remain missing and will not be imputed.

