4.2 Complementary Information on Derived Endpoints: Calculation Methods

4.2.1 Safety

4.2.1.1 Solicited Reactions

4.2.1.1.1 Daily Intensity

All daily records for solicited reactions will be derived into daily intensity according to the following classification: None, Grade 1, Grade 2, Grade 3, or Missing (Unknown).

For the derivation of daily intensities, the following sequential steps will be applied:

- 1. Solicited reactions (except Fever/Pyrexia) with CRF presence recorded as "No" and with all daily records missing (Unknown) then all daily intensities will be derived as None.
- 2. For non-measurable solicited reactions, daily intensities will correspond to daily records reported in the clinical database. For measurable solicited reactions the daily measurements reported in the clinical database will be converted based upon the intensity scales defined in the protocol; this assumes a reaction that is too large to measure (non-measurable, "NM") is Grade 3. Note the intensity could be considered "None" (not a reaction) in the analysis despite being considered a reaction by the investigator (e.g., swelling measurement > 0 mm but < 25 mm in adults).

Note: The maximum intensity on the ongoing period is derived from the record of the maximum intensity/measurement after the end of the solicited period following the rule described above.

Table 4.1: Solicited injection site reactions: terminology, definitions, and intensity scales – Infants and toddlers aged ≤ 23 months

CRF term (MedDRA	Injection site tenderness	Injection site erythema	Injection site swelling
lowest level			
term [LLT])			
Diary card	Tenderness	Redness	Swelling
term			
Definition	mobilized	including the approximate point of needle entry	Swelling at or near the injection site Swelling or edema is caused by a fluid infiltration in tissue or cavity and, depending on the space available for the fluid to disperse, swelling may be either soft (typically) or firm (less typical) to touch and thus can be

			best described by looking at the
			size of the swelling
Intensity	Grade 1: Minor reaction when	Grade 1: > 0 to < 25 mm	Grade 1: > 0 to < 25 mm
scale*	injection site is touched	Grade 2: \geq 25 to	Grade 2: \geq 25 to \leq 50 mm
	Grade 2: Cries or protests	< 50 mm	Grade $3: \ge 50 \text{ mm}$
	when injection site is touched	Grade $3: \ge 50 \mathrm{mm}$	
	Grade 3 (CRF): Cries when		
	injected limb is mobilized, or		
	the movement of the injected		
	limb is reduced		

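### SAP 4.2.2.6 counts an unsolicited AE of missing grade that caused discontinuation but not a solicited reaction of missing grade, so the SOC/PT table can omit an event that the other tables count

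*SAP*

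**What the plan says.** SAP 4.2.2.6 defines how three tables identify AEs leading to discontinuation.

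- **Disposition.** The completion form decides alone: "Disposition table: A participant who, on the 'Completion at End of Study' form question 'What was the participant's status?' has 'Adverse Event' checked". Grade plays no part.
- **Safety overview.** There are two routes: the form status or a marked event. A participant counts who "has 'Adverse Event' checked or lists a solicited AE that has 'Caused Study Termination' checked that is at least Grade 1", or who has a marked unsolicited AE meeting the wider condition below.
- **SOC/PT.** Only marked events count, with no route through the form: "a solicited AE that has 'Caused Study Termination' checked that is at least Grade 1 or an unsolicited AE". The unsolicited AE qualifies if it is "checked that is at least Grade 1 or missing and is within the time period indicated".

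On missing grades, SAP 3.4.4.1.3 says "For solicited reactions, missing intensities will be handled as described in Section 4.2.1.1.1", whereas "For unsolicited AEs, missing intensities will remain missing and will not be imputed". SAP 4.2.1.1.1 lists Missing as a possible daily class and adds that "For non-measurable solicited reactions, daily intensities will correspond to daily records reported in the clinical database".

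**The concern.** Missing grade is accepted for one type of event and not for the other, although in both the site has recorded that the event ended participation. SAP 4.2.2.6 opens by saying this information is reported as it was collected, and dropping an event whose termination box was ticked does not do that. The SAP leans the other way elsewhere. An unsolicited systemic AE with no causality assessment is treated as related (3.4.4.1.2), and one with no start date at all is placed inside the 30-day window (4.2.1.2.4).

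Whether an AE led to early termination is among the items listed for the safety endpoints (SAP 3.4.3). Withdrawals are expected to be uncommon (Protocol 7.2), so a single event can change what the report says. At stake is agreement between tables, and in one configuration the visibility of a terminating reaction in any of the three.

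**Working it through.** No figure in the plan bears on this point, so there is none to reproduce. The check is a reading of the rules, followed by a small illustration.

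**Step 1. Can a solicited grade be missing at the time of analysis?** Yes, in a limited set of cases.

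- SAP 4.2.1.1.1 fills blanks in one situation: presence recorded as No and all daily records missing becomes None. Fever is excepted. No rule covers presence Yes with all days blank, or a fever with no recorded temperature.
- A reaction too large to measure is set to Grade 3, so it is not missing.
- SAP 4.2.1.1.2 takes the maximum of the daily intensities. On the natural reading, one day with a known intensity is enough for the maximum to be known.
- SAP 4.2.1.1.3 turns a missing maximum into missing presence.

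So the grade is missing essentially only when no day has a known intensity. SAP 3.4.4.1.3 refers such cases to 4.2.1.1.1, which does not resolve them.

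**Step 2. Apply 4.2.2.6 to each combination.** All events below carry the site's termination mark and fall in the time period.

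| Type | Grade | Form status is Adverse Event | Disposition | Overview | SOC/PT |
|---|---|---|---|---|---|
| Solicited | ≥ 1 | yes | counted | counted | counted |
| Solicited | ≥ 1 | no | not counted | counted | counted |
| Solicited | Missing | yes | counted | counted | **not counted** |
| Solicited | Missing | no | not counted | **not counted** | **not counted** |
| Unsolicited | Missing | yes | counted | counted | counted |
| Unsolicited | Missing | no | not counted | counted | counted |

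The two solicited rows with missing grade differ from their unsolicited counterparts in the bold cells only.

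**Step 3. Admit missing grade for solicited AEs.** Row three changes in SOC/PT. Row four changes in the overview and SOC/PT. No other row changes. An event graded None stays out of SOC/PT for both types, and enters the overview only through the form status.

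**Step 4. What one event would do (assumed, not predicted).** Denominators are planned enrolment (446 in total, 223 per main age group; Protocol 9.2). The actual denominator is the safety analysis set. Exact (Clopper-Pearson) limits:

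- Zero events: upper limit 1 − 0.025^(1/n). For n = 446, 0.82%; for n = 223, 1.64%.
- One event: lower limit 1 − 0.975^(1/n); upper limit is the p at which P(X ≤ 1) = 0.025. For n = 446, 1/446 = 0.22% (0.01% to 1.24%); for n = 223, 1/223 = 0.45% (0.01% to 2.47%).

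**The case against.** **The asymmetry follows the SAP's own definitions.** Presence of a solicited reaction is derived from its intensity, so a missing grade means missing presence (4.2.1.1.3). An unsolicited AE exists once it has a verbatim term and is not Grade 0 (4.2.1.2.1), so it is an event even without a grade. This explains the wording. It does not justify losing an event that the site marked as the reason for leaving. The Grade 1 condition does usefully remove measurements that grade as None, such as swelling under 25 mm in adults, but admitting missing grades leaves that exclusion intact.

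**The case should be rare.** The site interviews participants, clarifies incomplete diary entries and reports information the diary lacks (Protocol 8.3.2). The investigator is to grade each AE (10.2.5). Early terminators are to be contacted for the scheduled safety follow-ups, except those who refuse contact or are lost (7.2, Follow-up of Discontinuations). All of this stands. A reader might infer from diary review at Visit 2 (Table 1.1) that a terminating reaction will often lack a grade. The documents do not support that: they give no frequency, and the safeguards point the other way. They reduce the gap without closing it.

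**Most tables keep the participant.** A reader might also infer that such reactions disappear from the discontinuation tables altogether. They do not. The disposition table has no grade condition, and the overview counts anyone whose form status is 'Adverse Event', the natural status for someone who left because of a reaction. Loss from the overview needs a second inconsistency, for example a form that records withdrawal by the participant or parent.

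**The change does not make the tables agree in every case.** If the form status is not 'Adverse Event', the disposition table still omits the participant. This is correct and is carried into the fix.

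**Conclusion.** The point holds in a narrow form. As written, the SOC/PT table always omits a marked solicited reaction with no known daily intensity, and the safety overview omits it when the completion form gives another status. No other SAP rule repairs this. The consequence is a possible failure of the tables to reconcile and, in the mismatch case, a terminating reaction that none of the three shows.

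The size cannot be computed. The comparison of zero with one event assumes that one such case occurs, and it is not evidence that tolerability will be reported too favourably. The conclusion rests on reading the words on missing grade as attached to unsolicited AEs only, which is how both bullets are built, and on the maximum being known once any day is known. This is a small clarification of a stated rule.

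**What to change.** In the safety overview and SOC/PT bullets of SAP 4.2.2.6, count a solicited AE marked as causing termination when its grade is at least 1 or missing, as is already done for unsolicited AEs. Show the intensity as Missing. Keep reactions graded None excluded. Add a footnote that such a reaction still has missing presence in the solicited-reaction tables under 4.2.1.1.3, so it can appear in the discontinuation table and not in its own endpoint table.

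The cost is a few words in two bullets, a footnote and one condition in the program; no data collection is added. The discontinuation count may rise slightly. The disposition table can still differ from the other two when the form status is not 'Adverse Event'.

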4.2.3 Immunogenicity

4.2.3.1 Computed Values for Analysis

In order to appropriately manage extreme values (undetectable responses < the lower limit of quantitation [LLOQ] and \ge the upper limit of quantitation [ULOQ]) for analysis purposes, the following computational rule is applied to the values provided in the clinical database for each blood sample drawn:

- If a value is < LLOQ, then use the computed value LLOQ/2
- If a value is between \geq LLOQ and \leq ULOQ, then use the value
- If a value is \geq ULOQ, then use the computed value ULOQ

4.2.3.2 Seroprotection

hSBA vaccine seroprotection is defined as: hSBA titers ≥ 1.8 .

4.2.3.3 Fold-rise

The derived endpoint fold-rise is driven by both baseline and post-baseline computed values and is computed as follows. Generally, for extreme values, this algorithm minimizes the numerator and maximizes the denominator.

- If the baseline computed value is < LLOQ and the post-baseline computed value is < LLOQ, then the fold-rise is 1
- If the baseline computed value is ≥ LLOQ and the post-baseline computed value is ≥ LLOQ, then the fold-rise is post-baseline computed value / baseline computed value
- If the baseline computed value is ≥ LLOQ and the post-baseline computed value is < LLOQ, then the fold-rise is (LLOQ/2) / baseline computed value
- If the baseline computed value is < LLOQ and the post-baseline computed value is ≥ LLOQ, then the fold-rise is post-baseline computed value /LLOQ

Note: If baseline or post-baseline is missing, then fold-rise is missing.

4.2.3.4 A/C/Y/W Vaccine Seroresponse

hSBA Vaccine seroresponse for serogroups A, C, Y, and W is defined as either:

- Post-vaccination hSBA titers $\geq 1:16$, if pre-vaccination hSBA titers $\leq 1:8$ or
- At least a 4-fold increase in hSBA titers from pre- to post-vaccination, if pre-vaccination hSBA titers ≥ 1:8.

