#### 8.1.2 Immunogenicity Assessments

Functional meningococcal antibody activity against serogroups A, C, Y, and W will be measured in a serum bactericidal assay utilizing the human complement (hSBA). Results will be expressed as antibody titer, geometric mean titers (GMTs), seroprotection and hSBA vaccine seroresponse.

hSBA vaccine seroresponse for serogroups A, C, W, and Y is defined as:

- For a participant with a pre-vaccination titer < 1:8, the post-vaccination titer must be ≥ 1:16
- For a participant with a pre-vaccination titer ≥ 1:8, the post-vaccination titer must be at least 4-fold greater than the pre-vaccination titer

Two-fold dilutions of test sera are prepared in sterile 96-well microtiter plates. Serogroup-specific meningococcal bacteria along with human complement are added to the serum dilutions and allowed to incubate. After this incubation period, an agar overlay medium is added to the serum/complement/bacteria mixture, allowed to harden, and then incubated overnight at 37°C with 5% carbon dioxide (CO2). Bacterial colonies present in the wells are then counted. The endpoint titer is determined by the reciprocal serum dilution yielding  $\geq$  50% killing as compared to the mean of the complement control wells. The lower limit of quantification (LLOQ) of the hSBA assay is a titer of 1:4.

Assays will be performed at Global Clinical Immunology (GCI), Swiftwater, Pennsylvania, USA.

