#### 9 Statistical Considerations

Clinical data will be analyzed under the responsibility of the Biostatistics Platform of the Sponsor.

A statistical analysis plan (SAP) will be written and peer reviewed before any analyses. In accordance with the protocol, the SAP will describe all analyses to be performed by the Sponsor and all the conventions to be taken.

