3.4.2 Immunogenicity Endpoint

No statistical hypotheses will be tested. Descriptive statistics will be provided for the antibody titers against meningococcal serogroups A, C, W, and Y by using hSBA before and 30 days after a single dose of meningococcal conjugate vaccine.

.

All immunogenicity analyses will be performed on the PPAS and the FAS.

In general, categorical variables will be summarized and presented by frequency counts, percentages, and CIs. The 95% CIs of point estimates will be calculated using the normal approximation for quantitative data and the exact binomial distribution (Clopper-Pearson method) for percentages. For GMTs, 95% CIs of point estimates will be calculated using normal approximation assuming they are log10-normally distributed.

Descriptive analyses of antibody responses to A, C, W, and Y serogroups using hSBA will include but not be limited to:

- hSBA seroprotection rate (titer $\geq 1:8$) and 95% CI
- GMTs and 95% CI.
- Titer distribution and reverse cumulative distribution curves (RCDCs)
- Percentage of participants with titers ≥ 4-fold rise from pre-vaccination to post-vaccination, and 95% CI
- Percentage of participants with hSBA titers \geq 1:4, and 95% CI
- Percentage of participants with hSBA vaccine seroresponse, and 95% CI Note: hSBA vaccine seroresponse for serogroups A, C, W, and Y is defined as:
- For a participant with a pre-vaccination titer < 1:8, the post-vaccination titer must be $\geq 1:16$
- \circ For a participant with a pre-vaccination titer $\geq 1:8$, the post-vaccination titer must be at least 4-fold greater than the pre-vaccination titer

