3.6 Data Monitoring Committee (DMC)

Not applicable.

4 Complementary Information on Assessment Methods

Study assessments and procedures are detailed in Section 8 of the protocol. This section focusses on complementary/additional information not detailed in the protocol.

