4.2.5.4 Duration of the Study

The durations are computed in days as follows: Latest period date - Earliest period date + 1.

5 Changes in the Conduct of the Trial or Planned Analyses

COVID FORM was not applied to the study as due to administrative issues study was pushed further and started only after when COVID was no more of a Pandemic.

For this study, screening failure information were not supposed to be collected according to the protocol. But inadvertently, this information was collected by the site, and it was integrated into several raw databases. This was due to fast recruitment in short period of time. The screen failures will be excluded from the main analysis. Their information will be presented in separate listing. The screen failures list was retrieved by the programming team and later was validated by the investigator. Sanofi team identified this issues and retraining was insured. But, the majority of recruitment was completed by then.

6 Supporting Documentation

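### Does SAP 4.2.3.4 count a rise from 1:8 to 1:16, only 2-fold, as a seroresponse?

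*SAP*

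**What the plan says.** Seroresponse is defined in four places.

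- **SAP 4.2.3.4** gives two alternatives. A post-vaccination titer of at least 1:16 suffices "if pre-vaccination hSBA titers $\leq 1:8$ or" the second alternative is met: "At least a 4-fold increase in hSBA titers from pre- to post-vaccination, if pre-vaccination hSBA titers ≥ 1:8".
- **SAP 3.4.2**, the SAP's section on the immunogenicity endpoint, separates the branches: "For a participant with a pre-vaccination titer < 1:8, the post-vaccination titer must be $\geq 1:16". Baselines of 1:8 and above need a 4-fold rise.
- **Protocol 8.1.2** gives the same split: "For a participant with a pre-vaccination titer < 1:8, the post-vaccination titer must be ≥ 1:16".
- **Protocol 9.4.2** repeats it, again with a baseline cut of < 1:8.

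Three further places bear on which definition governs. Protocol Section 9 ties the SAP to the protocol: "In accordance with the protocol, the SAP will describe all analyses to be performed by the Sponsor". SAP Section 4 opens by limiting its own role: "This section focusses on complementary/additional information not detailed in the protocol". SAP Section 5, headed "Changes in the Conduct of the Trial or Planned Analyses", covers the COVID form and the screen-failure records and says nothing about seroresponse.

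**The concern.** SAP 4.2.3.4 sits among the calculation methods, where a programmer would look for the derivation. As printed, its branches overlap at a baseline of exactly 1:8, and meeting either one is enough. The assay uses two-fold dilutions, so 1:8 and 1:16 are adjacent reportable titers and the case can occur. A participant who moves up one dilution step would count as a responder there and as a non-responder under SAP 3.4.2 and Protocol 8.1.2. The difference works in one direction only: the seroresponse rate could rise, never fall. Seroresponse is reported for four serogroups, overall and by age, on both the PPAS and the FAS, so a wrong rule would carry through many tables.

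**Working it through.** **Inputs.** Two-fold dilutions and an LLOQ of 1:4 (Protocol 8.1.2); fold-rise rule (SAP 4.2.3.3); evaluable numbers of 400 overall and 200 per age category (Protocol 9.2, SAP 3.2). The plan gives no figure of its own to reproduce on this point.

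**Step 1: where the two readings differ.** Titers are written as reciprocals.

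| Baseline | Response with < 1:8 | Response with ≤ 1:8 as printed |
|---|---|---|
| below 4 | post ≥ 16 | post ≥ 16 |
| 4 | post ≥ 16 | post ≥ 16 |
| 8 | post ≥ 4 × 8 = 32 | post ≥ 16 |
| 16 or more | post ≥ 4 × baseline | post ≥ 4 × baseline |

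Only the row for baseline 8 differs. No reportable titer lies between 16 and 32, so the single discordant pair is (8, 16), with fold-rise 16/8 = 2. Full enumeration on a grid from below 4 up to 8192 gives the same single pair. Neither document states the ULOQ, but capping the grid anywhere from 64 to 8192 does not change the result.

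**Step 2: which reading fits the rest of the plan.** Under < 1:8, seroresponse coincides with the separately planned percentage with a fold-rise of at least 4, using SAP 4.2.3.3:

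- Baseline below 4: post/4 ≥ 4, so post ≥ 16.
- Baseline 4: post/4 ≥ 4, so post ≥ 16.
- Baseline 8 or more: the criterion is the 4-fold rule itself.

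Under ≤ 1:8 the two endpoints part at (8, 16). The second branch in SAP 4.2.3.4 also assigns a baseline of 1:8 to the 4-fold criterion, which would have no effect at that titer if the first branch already accepted 1:16.

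**Step 3: how far the sign can be trusted.** The available SAP text was read from PDF by a program. In SAP 4.2.3.4 the doubtful sign lies inside a fragment converted to mathematical notation; the second branch, with a plain ≥, was not converted. In SAP 3.4.2 the < before 1:8 is plain text, outside the converted part. Signs are doubtful elsewhere too:

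- SAP Table 4.1, Grade 2 swelling, has an upper bound of ≤ 50 mm although Grade 3 begins at ≥ 50 mm. The adjacent erythema cell and the swelling cell in Protocol Table 10.1 have < 50 mm. This is the same substitution of ≤ for <.
- SAP 4.2.3.1 reads "If a value is between \geq LLOQ and \leq ULOQ, then use the value", and its next line assigns values ≥ ULOQ to the ULOQ. The overlap is harmless because both lines return the ULOQ, but < was expected.
- SAP 4.2.3.2 prints 1.8 where SAP 3.4.2 and 4.1 have 1:8.
- Protocol 9.4.2 prints > 1:16 where Protocol 8.1.2 and SAP 3.4.2 have ≥ 1:16.

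**Step 4: size if the sign were real.** The expected rise per serogroup is P(pre = 1:8) × P(post = 1:16 given pre = 1:8). The documents give neither probability. Each affected participant adds 100/400 = 0.25 points overall, or 100/200 = 0.5 points in an age category. Purely as an assumption, shares of 1%, 2% and 5% of 200 would add 2, 4 and 10 responders. Starting from an assumed 160/200 (80.0%, Clopper-Pearson 95% CI 73.8 to 85.3), the rate would become 162/200 (81.0%, 74.9 to 86.2), 164/200 (82.0%, 76.0 to 87.1) or 170/200 (85.0%, 79.3 to 89.6).

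**The case for a change.** The strongest case for the concern is that the printed text does conflict, and in the section a programmer would use. Extraction damage is likely but not proved: SAP 4.2.3.4 is running text rather than a broken table, and < survives elsewhere in the SAP, including in the same criterion in 3.4.2. The statements on the SAP's relation to the protocol show what was intended; they do not themselves correct a derivation rule. Confirming one symbol would cost almost nothing.

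Part of this stands. The logic is right: a genuine ≤ would misclassify the pair (1:8, 1:16), and the available text cannot exclude that. What does not stand is the step from a doubtful sign to a defect in the plan. The concern is true only if the original shows ≤, and the closest parallel in the same SAP, the swelling cell, has the same sign in a place where it cannot be right. If the original shows <, nothing needs to change. Comparing seroresponse with the 4-fold percentage would expose the pair, but only if the fold-rise is coded as in SAP 4.2.3.3: a plain ratio with values below 1:4 coded as 2 would also flag a move from below 1:4 to 1:8. Such a check is an option for the programming team and does not remedy any shown error.

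**Conclusion.** The concern does not hold. The baseline cut for seroresponse is < 1:8 in Protocol 8.1.2, Protocol 9.4.2 and SAP 3.4.2, and the second branch of SAP 4.2.3.4 points the same way. The one contrary sign is more likely a reading artefact than a different rule. This conclusion rests on the pattern of doubtful signs in the available text and on the absence of any recorded change to the definition; the original page was not available.

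If the sign did prove genuine, it would be a one-symbol slip affecting a single titer pair of unknown frequency. GMTs, the rates at 1:4 and 1:8, and the 4-fold rate would be unchanged. The study tests no hypothesis, so no error rate, power or sample size is involved.
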